7.2.2 Secondary Safety Endpoints

The following safety parameters will be evaluated for the duration of the study:

- Type, frequency, severity, and relationship of AEs to investigational product (IP)
- Number of subjects who discontinue IP due to any AE
- Frequency of clinically significant changes in vital signs and/or laboratory findings

7.3 Exploratory Endpoints (Efficacy)

Exploratory efficacy endpoints

- The proportion of subjects who are in clinical remission per the MMS, as applicable, over time
- The proportion of subjects who are in clinical response per the MMS, as applicable, over time
- The proportion of subjects achieving an RBS ≤ 1 over time, except at Week 8
- The proportion of subjects achieving Stool Frequency sub-score [SFS] ≤ 1 over time
- The change from baseline in the MMS at Week 2, at Week 4, and at Week 8

- Change from baseline in the Ulcerative Colitis Endoscopic Index of Severity (UCEIS) endoscopic score
- The change from baseline in the Geboes Index, Robarts Index, and Nancy Index at Week 8

7.4 Exploratory Endpoints (Other)

PK Endpoint:

• The population-based PK estimates of GED-0507-34-Levo

PD/Biomarker Endpoints:

- The change from baseline in CRP concentration over time
- The change from baseline in FCP concentration over time
- The correlation between FCP/CRP and clinical outcomes over time

8 OVERALL STUDY DESIGN

8.1 Study Design

This is a Phase 2, multicenter, randomized, double-blind, placebo-controlled, parallel-group study to evaluate the efficacy and safety of 2 doses of GED-0507-34-Levo in subjects with active, mild-to-moderate UC (defined as an MMS of ≥ 4 to ≤ 8 , with a Stool Frequency subscore ≥ 1 , an RBS = 1 or 2, and an endoscopic sub-score ≥ 1 and ≤ 3).

Approximately 207 subjects (69 subjects per arm) will be randomized in a 1:1:1 ratio using an Interactive Web Response System (IWRS) to receive oral GED-0507-34-Levo (80 mg BID) or 160 mg BID) or identically appearing placebo BID for up to 8 weeks. Treatment will be assigned via IWRS.

The study will consist of 3 parts:

- In Part 1, 24 subjects will be randomized with 8 subjects per treatment group. The Safety evaluation (clinical, hematological, and biochemistry) on these 24 subjects will be assessed by an Independent Safety Committee.
- After the 24th subject is enrolled in Part 1, then Part 2 will start in which new subjects will be randomized only in the 80 mg BID and placebo groups in a 1:1 ratio.
- Once the 24 subjects in Part 1 have completed 8 weeks of treatment and the Safety evaluation has been completed with no safety concerns, then Part 3 will continue to enroll subjects randomized into all 3 treatment groups. An unequal randomization will be used in Part 3 of the study in order to ensure approximately equal numbers of subjects randomized into each of the 3 treatment groups across the 3 study parts.

The study will consist of 3 phases:

- Screening Phase up to 4 weeks
- Double-blind Placebo-controlled Phase Week 0 to Week 8
- Follow-up Phase Week 9

8.1.1 Safety/PK Sub-studies

Safety will be assessed on the first 24 randomized subjects (8 in 160 mg/day, 8 in 320 mg/day, and 8 in Placebo group) by an Independent Safety Committee before more subjects in the high dose group are enrolled in the study.

After enrollment of subject number 24, and until the Independent Safety Evaluation is complete, enrollment will continue and subjects will be randomized in the placebo and 80 mg BID (160 mg/day) dose groups.

Upon completion of the Independent Safety Evaluation and provided a positive safety outcome is obtained, enrollment of subjects in the 3 dose groups will be performed until end of study.

A PK sub-study will be conducted at selected sites. The target for the PK sub-study is to achieve participation of approximately 50% of the randomized subjects

8.1.2 Double-blind Placebo-controlled Phase

Eligible subjects will enter the Double-blind Placebo-controlled Phase for 8 weeks, at the Baseline Visit (Week 0, Visit 2). Subjects will be randomly assigned to study treatment as described above. All subjects will receive high-density polyethylene (HDPE) bottles of identical appearance to maintain blinding. Subjects will continue to receive the treatment assigned at baseline for 8 weeks.

8.2 Internal PPM SERVICES SA Safety Monitoring During the GED-0507-34-Levo Program

In addition to ongoing safety monitoring conducted by Investigators and individual study personnel, cumulative and interval blinded AEs, SAEs, discontinuations due to AEs, and abnormal laboratory findings will be reviewed internally by the Safety Management Team (SMT). The review follows the Council for International Organizations for Medical Sciences, Working Group VI (CIOMS VI) recommendations. The SMT is comprised of lead representatives from multiple PPM SERVICES SA functions engaged in the GED-0507-34-Levo development program. The scope, conduct, processes, and accountabilities of the SMT are specified in the SMT charter.

8.3 Internal Data Safety Monitoring Board During the Study

Unblinded safety data will be reviewed periodically by an internal data safety monitoring board (DSMB) at PPM SERVICES SA that is independent of the study team. The external data monitoring committee (DMC; Section 8.4) may be convened ad hoc at the request of the DSMB.

8.4 External Safety and Efficacy Monitoring During GED-0507-34-Levo Program

Monitoring will also be performed by an independent, external DMC that will assess safety as outlined in the DMC charter (available upon request) after 24 randomized subjects: 8 treated with 160 mg/day (80 mg BID), 8 with 320 mg/day (160 mg BID), and 8 with placebo. The DMC is comprised of 3 independent external trialists and an independent, external statistician, for whom there is no identified conflict of interest. The DMC will be convened approximately every 12 months or ad hoc at the request of the DSMB or SMT. The DMC scope, conduct, processes, and accountabilities are pre-specified in its charter. Recommendations of the DMC based on the overall benefit/risk evaluation may include proceeding with the study per protocol, proceeding with the study with modification, or study suspension.

8.5 Study Design Rationale

This study represents the second investigation of GED-0507-34-Levo in subjects with UC. This study will provide information on the safety and clinical efficacy in the UC population prior to advancing to larger clinical trials, as well as provide critical information for the design of future studies in this population.

The purpose of this study is to determine whether GED-0507-34-Levo is effective and safe in the treatment of subjects with active UC. The primary measure of efficacy will be clinical remission determined by the MMS in a double-blind, placebo-controlled study at Week 8. Clinical remission is defined as an MMS \leq 2, with no individual sub-score > 1, at Week 8. The laboratory results, AEs, vital signs, ECGs, pregnancy tests, and physical examinations will be monitored to evaluate safety.

A schematic diagram illustrating the study design is shown in Figure 1.

8.6 Study Duration

Subjects will spend up to 13 weeks in this study: up to 4 weeks in the Screening Phase; 8 weeks in the Double-blind Placebo-controlled Phase; and 1 week in the Follow-up Phase.

8.7 End of Trial

The End of Trial is defined as either the date of the last visit of the last subject to complete the study or the date of receipt of the last data point from the last subject that is required for primary, secondary, and/or exploratory analysis, as pre-specified in the protocol and/or the Statistical Analysis Plan (SAP), whichever is the later date.

Figure 1: Overall Study Design

[figure not shown]

Table 1Schedule of Events

	Screening Phase		Follow-up Phase					
Visit Number		2 Baseline Visit	3	ouble-blind Pla	5	6	7 End of Treatment/ Early Termination Visit ^a	8
Week	-4 to -1	0 (Day 1)	1 (Day 7)	2 (± 3 days)	4 (± 3 days)	6 (± 3 days)	8 (± 3 days)	9 (± 3 days)
Informed Consent	X		(13)		((,,	(2 223, 27
Inclusion / Exclusion Criteria	X	X						
Medical History	X							
Prior / Concomitant Medications	X	X	X	X	X	X	X	X
Pregnancy Test and Contraception Education b	X	X	X	X	X	X	X	X
Hepatitis B and C Tests	X							
Clinical Lab Evaluations	X	X			X		X	X
Stool Culture / Microscopy	X							
Height	X							
Vital Signs / Weight	X	X			X	X	X	X
Physical Exam	X	X					X	X
Adverse Events	X	X	X	X	X	X	X	X
12-lead ECG	X		X	X			X	
PK Draw at Selected Sites ^c				X	X	X	X	
Subject Diary for UC Disease Activity	X	X	X	X	X	X	X	
MMS	X	X	X	X	X	X	X	
Endoscopy d,e	X						X	
PGA	X						X	
TMS	X						X	
Intestinal Mucosal Biopsies f	X						X	

	Screening Phase		Follow-up Phase					
Visit Number	1	2 Baseline Visit	3	4	5	6	7 End of Treatment/ Early Termination Visit ^a	
Week	-4 to -1	0 (Day 1)	1 (Day 7)	2 (± 3 days)	4 (± 3 days)	6 (± 3 days)	8 (± 3 days)	9 (± 3 days)
Fecal Calprotectin	X	X	X		X	X	X	
CRP	X	X	X		X	X	X	
Dispense IP		X			X			
Return and Count IP		X	X	X	X	X	X	

CRP = high sensitivity C-reactive protein; ECG=electrocardiogram; ET= Early Termination Visit; IP = Investigational Product; MMS = Modified Mayo score; PK = pharmacokinetics; PGA= Physician's Global Assessment; TMS = Total Mayo Score; UC = ulcerative colitis.

- a. Subjects who discontinue from the study prior to the Week 8 Visit will have an Early Termination Visit.
- b. The female subject's chosen form of contraception must be effective by the time the female subject is randomized into the study (for example, hormonal contraception should be initiated at least 28 days before randomization). Serum pregnancy tests will be performed at screening, and urine pregnancy testing will be done at all remaining visits, including an Early Termination Visit. Urine pregnancy test kits will be provided to the site. A pregnancy test(s) should be administered if the subject misses a menstrual period during the study treatment period.
- c. Sparse PK samples as described in Section 9.9.1.
- d. The screening endoscopy will consist of a colonoscopy or flexible rectosigmoidoscopy. Colonoscopy is required at screening only for those subjects who have not had a colonoscopy within 12 months prior to the Screening Visit. Rectosigmoidoscopies will be repeated at Week 8 or at the Early Termination Visit.
- e. Rectosigmoidoscopy will not be repeated if within 4 weeks of the previous endoscopy.
- f. Two intestinal mucosal biopsies will be performed with the endoscopy during the Screening Phase and also at the Week 8 Visit or the Early Termination Visit if the subject discontinues prior to Week 8. Biopsies should be taken from the most inflamed area of the rectum or rectosigmoid junction, while avoiding ulcerated mucosa. Week 8 biopsies should be taken from the same location as the baseline biopsy.

9 PROCEDURES

The following procedures/assessments will be conducted according to the schedule indicated in Table 1 Schedule of Events.

9.1 Informed Consent

An informed consent form (ICF) must be signed by the subject before any study-related assessments are performed. In addition, the randomized subjects must consent specifically for the PK sub-study. Details of the informed consent process may be found in Section 17.3.

9.2 Contraception Education

The risks to a fetus or to a nursing child from GED-0507-34-Levo are not known at this time.

A female of childbearing potential (FCBP) is a sexually mature female who 1) has not undergone a hysterectomy (the surgical removal of the uterus) or bilateral oophorectomy (the surgical removal of both ovaries) or 2) has not been postmenopausal for at least 24 consecutive months (that is, has had menses at any time during the preceding 24 consecutive months).

All FCBP must use one of the approved contraceptive options as described in Section 10.2 while on IP and for at least 28 days after administration of the last dose of the IP.

At the time of study entry, and at any time during the study when an FCBP's contraceptive measures or ability to become pregnant changes, the Investigator will educate the subject regarding contraception options and correct and consistent use of effective contraceptive methods in order to successfully prevent pregnancy.

9.3 Medical and Disease History

Relevant medical history should be recorded, including caffeine consumption, smoking and alcohol history, as well as previous relevant surgeries. Disease history includes history of UC (i.e, the disease under study).

9.4 Inclusion/Exclusion Criteria

Subjects must meet all inclusion criteria (Section 10.2) and must not have any of the conditions specified in the exclusion criteria (Section 10.3) to qualify for participation in the study. The subject's source documents must support his/her qualifications for the study (eg, if a female subject does not require pregnancy testing and birth control because of a hysterectomy, the date of the hysterectomy must be included in the medical history).

9.5 Prior/Concomitant Medications and Therapies

All medications (prescription and nonprescription, including vitamins) taken by the subject up to 30 days prior to the Screening Visit (Visit 1) should be recorded, including the stop dates for medications prohibited in the study. All medications taken by the subject at any time during the

study must also be recorded. Other key medications and therapies, such as previous treatment for tuberculosis or relevant diseases, should also be recorded.

9.6 Safety Assessments

9.6.1 Serum and Urine Pregnancy Tests for Females of Childbearing Potential

A urine pregnancy test will be performed on all FCBP at the Baseline Visit, all onsite visits, and at Follow-up or at the Early Termination Visit. A urine pregnancy test kit will be provided by the central laboratory. Pregnancy tests should be performed if the FCBP has missed a menstrual period or the contraception method has changed.

9.6.2 Hepatitis B and C

The hepatitis screen includes testing for hepatitis B surface antigen and antibody, hepatitis B core antibodies (immunoglobulin G [IgG]/immunoglobulin M [IgM]), and antibodies to hepatitis C.

9.6.3 Vital Signs, Height, and Weight

Vital signs, including temperature, pulse, and seated blood pressure, will be taken during the visits indicated in Table 1 Schedule of Events. Height will be measured and recorded at screening; weight will also be measured and recorded at screening and then as indicated in Table 1 Schedule of Events. Body mass index (BMI) will be calculated at screening.

9.6.4 Physical Examinations

Complete physical examinations will include evaluation of the skin, respiratory, cardiovascular, abdominal, neurological, lymphatic, and musculoskeletal systems. Results of the physical examinations will be recorded only in the source documents.

Clinically significant abnormal findings (with the exception of the disease under study [UC]) identified prior to first dose of IP will be recorded on the electronic case report form (eCRF) as medical history; clinically significant findings after the first dose of IP will be recorded as AEs.

Note: Gynecological and urogenital examinations will not be performed unless for cause.

9.6.5 Stool Culture / Microbiology

Stool culture analysis and assessment of *Clostridium difficile* toxin will be performed at the Screening Visit, as well as *Salmonella, Shigella, Yersinia, Aeromonas, Plesiomonas*, or *Campylobacter*. Subjects who are initially positive for *C. difficile* may re-screen for the study after they have successfully completed therapy and had 2 months of consecutive negative tests for C. *difficile*.

9.6.6 12-lead Electrocardiogram

The 12-lead ECG will be performed after the subject has been supine for approximately 3 minutes. Sites are to utilize their own local ECG machines for the study, and the automated ECG readings will be further interpreted by the Investigator by clinically correlating them with the subject's condition. The Investigator's clinical interpretation will be recorded in the eCRF as one of the following: "normal", "abnormal, not clinically significant", or "abnormal, clinically significant". "Abnormal, clinically significant" results should be recorded in the Medical History eCRF if found prior to the first dose of IP or in the AE eCRF if found after the first dose of IP.

9.6.7 Clinical Laboratory Evaluations

A central laboratory will be used for this study. Clinical laboratory evaluations will include the following:

- Hematology: complete blood count (red blood cell [RBC] count, hemoglobin, hematocrit, white blood cell [WBC] count and differential, absolute WBC counts, platelet count)
- Serum chemistries: total protein, albumin, calcium, phosphorous, glucose, total cholesterol, high-density lipoprotein (HDL) cholesterol, low-density lipoprotein (LDL) cholesterol, triglycerides, uric acid, total bilirubin, alkaline phosphatase, aspartate aminotransferase (AST)/ serum glutamic oxaloacetic transaminase (SGOT), alanine aminotransferase (ALT)/ serum glutamic pyruvic transaminase (SGPT), sodium, potassium, chloride, carbon dioxide, blood urea nitrogen (BUN), creatinine, lactate dehydrongenase (LDH), magnesium, amylase (pancreatic)
- Urinalysis: dipstick urinalysis (specific gravity, pH, glucose, ketones, protein, blood, bilirubin, leukocyte esterase, nitrite, and urobilinogen)
 - Microscopic urinalysis (epithelial cells, RBC, WBC, and casts) will be performed only if the dipstick urinalysis is abnormal

Note: Clinical laboratory evaluations are not required to be fasting. However, the site will record whether a clinical laboratory evaluation was fasting or nonfasting on the lab requisition form.

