5.3 Results of Clinical Studies in Humans

The clinical formulation of GED-0507-34-Levo is a solid dosage oral form, a gastro-resistant, pH-dependent release tablet designed for colonic release of the drug substance.

To date, the GED-0507-34-Levo clinical development program for the treatment of UC consists of 2 studies: Study GED-0507-01-09, a Phase 1 first-in-human, double-blind, placebo-controlled study of a single dose of GED-0507-34-Levo gastro-resistant prolonged release tablets, administered at rising doses in healthy volunteers to evaluate safety and pharmacokinetics (PK); and Study GED-0507-01-11, a Phase 2a multicenter, single-arm, single-stage, open-label, Fleming's design, early-escape design, proof-of-concept clinical study on the efficacy and safety of GED-0507-34-Levo, in patients with active UC. Treatment duration in the Phase 2a study was 8 weeks; one 80 mg tablet twice per day (BID) was administered, for a total daily dose of 160 mg per day.

In the Phase 1 study, no serious adverse events (SAEs) or suspected-unexpected serious adverse reactions (SUSARs) were reported during the study. Only 2 AEs were considered possibly related to study treatment: transient amylase value increase (shown to be salivary and not pancreatic) and headache. In the Phase 2a study, 5 AEs were considered possibly or probably related to study medication (possibly related: worsening of UC, stomach ache, nausea, increase of creatine phosphokinase [CPK]; probably related: worsening of abdominal symptoms); 3 AEs led to permanent discontinuation that were considered by the Investigator to be possibly related (worsening of underlying disease, nausea, and stomach ache) and 1 AE that was considered probably related (abdominal symptom) led to permanent discontinuation. The clinical safety results show that GED-0507-34-Levo is well tolerated, and there were no safety concerns in either of the 2 studies.

In a different therapeutic area, a Phase 1 clinical study was also performed in patients affected by psoriasis with GED-0507-34-Levo formulated as cream for topical administration (Study GED-0507-PSO-01-12). No SAE occurred during the study. GED-0507-34-Levo was well tolerated; no patient dropped out during the study and no safety concern was raised. Only one event ("redness and itch in both treated areas" in a subject of GED-0507-34-Levo 0.5% group) was defined as "probably related" to study drug.

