If a post-hoc revision of the Fleming's design and assumptions is performed based on the recently published figures, ie, considering the remission rates of 20% (Active Treatment) and 5% (Placebo), with a one-sided α of 5% and 90% power (1– β), then the revised protocol Fleming's design would recommend a sample size of 34 with a best cut-off of \geq 5 successes, that is the primary endpoint result of the intent-to-treat (ITT) population.

Moreover, analysis of the per-protocol (PP) population (remission rate 33.3%, clinical improvement rate 53.3% with UC-DAI total scores 6.9 [\pm 1.2, median 7] and 4.1 [\pm 3.1, median 4] at baseline and Week 8) suggests that GED-0507-34-Levo might be able to induce a clinically significant rate of remission of active UC and to improve general conditions as also suggested by the score of the physician's assessment of patient's condition (PP) that mirrors the improvements observed for the secondary endpoints: from 1.8 at baseline to 1.0 at Week 8 (-0.8).

Therefore, the current study GED0507-UC-001 was designed to evaluate the clinical efficacy of GED-0507-34-Levo (80 mg BID and 160 mg BID), compared with placebo, in subjects with active UC.

This study will be performed in compliance with the protocol, International Conference on Harmonisation (ICH) Good Clinical Practice (GCP), and applicable regulatory requirements.

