5.5 Benefit / Risk Assessment

GED-0507-34-Levo is a novel therapeutic product in clinical development for the treatment of patients with UC.

GED-0507-34-Levo is small molecule new chemical entity designed to selectively target inflammatory pathways. GED-0507-34-Levo anti-inflammatory activities have been demonstrated in vitro in several cell lines and in vivo in mouse models of induced colitis and compared to the activity mediated by 5-ASA, the standard treatment for mild-to-moderate UC. Both in vitro and in vivo GED-0507-34-Levo shows a higher anti-inflammatory activity as compared to 5-ASA in the non-clinical pharmacology studies. Non-clinical pharmacology studies have shown that GED-0507-34-Levo exerts its anti-inflammatory properties in intestinal epithelial cells through inhibition of production of pro-inflammatory mediators such as TNF- α and IL-8. This occurs via up-regulation of IkB α expression and consequent inhibition of NF- κ B activation in a PPAR γ -dependent manner.

Clinical safety data are available from the subjects enrolled in the completed Phase 1 and Phase 2a clinical studies. The clinical data collected so far were obtained with a gastro-resistant 80 mg tablet whose release was prolonged during time. Single doses up to 320 mg/day were tested in healthy volunteers in the Phase 1 study, and 8-week administration of 160 mg/day dose was tested in UC subjects in the Phase 2a trial. Adverse events considered possibly or probably related to GED-0507-34-Levo included transient amylase value increase (shown to be salivary and not pancreatic), headache, worsening of UC, stomach ache, nausea, increase of CPK, and worsening of abdominal symptoms. All related AEs were mild in intensity except the high amylase value, which was considered severe. Otherwise, GED-0507-34-Levo appeared to be safe and well tolerated.

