The present Phase 2 clinical study GED-0507-UC-001 will explore the efficacy and safety of 2 dose levels of GED-0507-34-Levo (80 mg BID and 160 mg BID), compared with placebo, in subjects with active UC. The doses have been selected mainly based on the results obtained in the completed Phase 2a Fleming design study. In the Phase 2a study GED-0507-34-Levo was well tolerated and, when the population of subjects who completed the 8-week treatment is taken into consideration, a 33% induction of remission rate is observed. However, many subjects either dropped out or withdrew early from the study, due to no effect or to worsening of the disease within the first 4 weeks of treatment. In the upcoming Phase 2 dose-finding study, in which a mild-to-moderate population will be included, the same dose of 160 mg/day used in the Phase 2a study (where a population with a higher severity grading was enrolled) and a higher (double) dose (320 mg/day) have been selected.

In the upcoming Phase 2 clinical trial, a slightly different oral formulation of GED-0507-34-Levo will be employed. The new formulation is a gastro-resistant delayed-release 80 mg tablet, designed as the previous one for the local delivery of the drug substance in the colon by making use of pH-dependent coating polymers. Based on the composition of the tablet, taking into consideration the PK profile of these colon release formulations with limited systemic exposure, and in analogy with 5-ASA formulations on the market (ie, 5-ASA-MMx and Asacol), no significant difference in the PK parameters with the GED-0507-34-Levo new formulation having an impact on safety are expected. However, to account both for the use of the new formulation and for the administration of a 320 mg/day dose (160 mg BID) for 8 weeks, as agreed during the pre-IND meeting (PIND) 126320, an Independent Safety Evaluation will be performed in an initial cohort of subjects before enrolling more subjects in the 320 mg/day (160 mg BID) high dose.

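### The scheduled chemistry panel omits CPK, although one mild, possibly related CPK increase was reported at 80 mg BID and this trial gives 320 mg/day for 8 weeks

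*Combined protocol and SAP*

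**What the plan says.** Section 9.6.7 sets out the central-laboratory tests. The serum chemistry list closes with "creatinine, lactate dehydrongenase (LDH), magnesium, amylase (pancreatic", and CPK does not appear in it. Table 1 schedules these tests at Screening, Baseline and Weeks 4, 8 and 9.

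Section 5.3 gives the Phase 2a safety results at one 80 mg tablet twice daily for 8 weeks. Five adverse events were attributed to treatment, among them "possibly related: worsening of UC, stomach ache, nausea, increase of creatine phosphokinase [CPK". Section 5.5 repeats the finding in the benefit/risk assessment ("stomach ache, nausea, increase of CPK, and worsening of abdominal symptoms") and grades it: "All related AEs were mild in intensity except the high amylase value, which was considered severe".

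On exposure, section 5.5 says that the Phase 2a dose is kept "and a higher (double) dose (320 mg/day) have been selected", and that "a slightly different oral formulation of GED-0507-34-Levo will be employed".

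Biochemistry results feed three planned uses: the Independent Safety Committee's evaluation of the first 24 subjects (section 8.1), the secondary safety endpoint on clinically significant laboratory changes (section 7.2.2), and the by-visit summaries and shift tables (section 13.7).

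**The concern.** One laboratory abnormality already attributed to the drug by an investigator is not followed by scheduled testing when the daily dose is doubled, the treatment period is 8 weeks and the tablet has changed. A CPK rise can occur without symptoms. Adverse event questioning and physical examination would then not reveal it, and section 14.3 can turn an abnormal value into an adverse event only if the value exists.

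At stake is descriptive safety information. The Phase 2a event came from a single-arm, open-label study, so it has no concurrent comparison. A randomised trial with a baseline draw and a placebo arm could put such an event in context, but only if CPK is measured.

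**Working it through.** The plan states no figure on this point to reproduce. The check sets sections side by side, with simple counts.

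**1. Is CPK measured anywhere?** I read the section 9.6.7 list through: proteins, minerals, glucose, lipids, uric acid, bilirubin, liver enzymes, electrolytes, renal markers, LDH, magnesium and pancreatic amylase. CPK is absent. Elsewhere in the document it occurs only in the abbreviation list (section 4) and as a past adverse event (sections 5.3 and 5.5). Table 1 has no separate row for it.

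**2. How many CPK events, and how serious?**
- Section 5.3 names four possibly related terms and one probably related term: 4 + 1 = 5, matching its stated total. One of the five is CPK.
- Related events leading to discontinuation: three "possibly related (worsening of underlying disease, nausea, and stomach ache", plus one probably related abdominal event, so 3 + 1 = 4.
- 5 − 4 = 1. The term left over is the CPK increase, reading worsening of the underlying disease as the same event as worsening of UC.
- By section 5.5 the CPK event was mild.

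**3. What exposure is new?**
- Phase 2a: 2 × 80 = 160 mg/day for 8 weeks.
- High-dose arm here: 2 × 160 = 320 mg/day for 8 weeks. Ratio 320/160 = 2, agreeing with the protocol's description.
- Section 5.5 records 320 mg/day before now only as single doses in healthy volunteers. On the visible documents, 8 weeks at that dose is new. Both active arms use the modified formulation.

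**4. What CPK data would each planned use receive?**

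| Use | Section | Scheduled CPK values |
|---|---|---|
| Part 1 evaluation, 24 subjects | 8.1, 13.10 | 0 |
| Clinically significant laboratory changes | 7.2.2 | 0 |
| Visit summaries and shift tables | 13.7 | 0 |

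**5. What would it take to collect them?** Five draws per subject are already scheduled. For about 207 subjects that is at most 5 × 207 = 1,035 assays, plus screening assays for subjects who are not randomised, whose number is not given. No visit or blood draw is added.

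**The case against.** The strongest reply is that this is a preference and not a defect. The trigger is one mild event, possibly related at most, from an uncontrolled study. Section 5.3 weighs the data and concludes that neither earlier study raised a safety concern. Nothing in the protocol promises scheduled testing for every laboratory term once called related. Section 5.5 expects limited systemic exposure and no formulation effect on pharmacokinetics that matters for safety. The event's CPK level, timing and confounders are not given, and section 5.3 refers further detail to the Investigator's Brochure. All of this stands, and it limits the point to a minor one.

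A second reply is that cover exists. AST, LDH, creatinine, potassium, phosphorus, dipstick blood with reflex microscopy and a musculoskeletal examination are all in the plan, and an investigator may order CPK at any time. This stands in part: clinically important consequences of a large rise might well be noticed. But none of these measures CPK, and ad hoc tests would be neither uniform across arms nor tied to a scheduled baseline. The safety committee charter, which is not visible, can direct the review of data, but the visible plan schedules no CPK result to review.

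A reader might also infer that the sponsor follows one earlier related laboratory finding, amylase, and has dropped the other. The documents do not support that. The related amylase rise was salivary and graded severe, whereas the panel measures pancreatic amylase. The panel therefore shows no policy of tracking earlier related findings from which CPK was left out.

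**Conclusion.** The point holds as a minor design improvement. The omission is plain on the text, the earlier event is documented, and the new exposure is real. The consequence is that scheduled testing would miss an asymptomatic CPK rise. Sample size, power, type I error and the efficacy analyses are unaffected.

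Two stronger readings should be resisted. First, a reader might infer that the Part 1 safety gate is defective. It is not: the gate reviews clinical, haematology and biochemistry data as planned, no stated rule is broken, and 8 high-dose subjects would say little about CPK even if it were measured. Second, a reader might build an event rate by dividing the one event by the Phase 2a sample. Section 5.4 says that a revised design "would recommend a sample size of 34 with a best cut-off of" 5 successes, but that number comes from the efficacy calculation. The number of subjects with CPK measured is not given, section 5.5 says that many subjects left early, and the background frequency of raised CPK is not stated. No rate or between-arm comparison can be projected from this.

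The conclusion assumes that no document outside those reviewed, such as the laboratory manual, already adds CPK.

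**What to change.** In section 9.6.7, add CPK to the serum chemistry list, to be assayed at the draws already in Table 1 (Screening, Baseline, Weeks 4, 8 and 9). Include the results in the Part 1 safety data and in the section 13.7 summaries and shift tables, to be read descriptively by arm. Clinically important values follow the existing rule in section 14.3, so no new threshold is needed.

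The cost is the assay fee and some incidental elevations, for example after exercise, which investigators at about 85 sites would have to judge and comment on. Baseline and placebo values would help in reading them.
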